## 6. DATA ANALYSIS

**6.2. Aim 2: Open pilot trial.** This is a small, single-arm, pilot feasibility trial to establish preliminary feasibility and acceptability of the intervention to inform intervention adaptations for a future randomized trial. This is not a randomized clinical trial to explore efficacy of treatment on outcomes. As such the analyses are focused on descriptive statistics. Frequencies and proportions will be calculated to assess feasibility outcomes. Feasibility outcomes are: recruitment feasibility (percent of participants who consent to screening; percent of participants meeting screening criteria; percent of eligible patients who consent); MBCT feasibility (percent of participants adherent to the MBCT intervention; percent of participants retained at post-intervention); videoconferencing feasibility (percent of connections dropped during sessions); and blood spot feasibility (percent of blood spot sample completion at baseline; percent of blood spot sample completion at post-intervention; percent of blood spot samples completed at follow-up; percent of adequate blood spot samples submitted). Means and standard deviations or medians and interquartile ranges will be calculated to assess acceptability ratings. Acceptability outcomes are rated from 0-10 with higher scores indicating greater acceptability and consist of: MBCT acceptability (helpfulness for mood; usefulness of session components); videoconferencing acceptability (ratings of videoconferencing ease of use; ratings of videoconferencing quality surveys; ratings of videoconferencing satisfaction); and blood spot acceptability (ease of blood spot collection; discomfort of blood spot collection).

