will be received by the RA, who will mark the date of receipt in the study database. Samples can be in ambient air for up to 2 weeks without degradation. We will ask participants to mail the samples within 24 hours of taking them to minimize the time samples are in ambient air. If samples are received beyond 2 weeks of the date indicated on the filter paper, we will ask participants to provide another sample, and participants will be made aware of this possibility in the consent form. Once received, the RA will bring the samples to be stored in a -20°C freezer in the MGH Clinical Research Center lab or mail them to our collaborator at the Laboratory for Human Biology Research at Northwestern University for storage and processing. Blood spots can be frozen at this temperature for several years without degradation.

When initially mailing the blood spot kit to participants, the RA will indicate the participant's study ID number on the filter paper. Participants will be informed not to write any personally identifying information on the filter paper. This will keep the blood samples de-identified.

Collecting whole blood spots with filter paper has been used in hospitals for decades to collect blood from newborns, and it has proven to be a safe and effective means for collecting and transporting samples in several large NIH-funded field-based studies. The Centers for Disease Control and Prevention have maintained independent quality control efforts and have reported that these approaches can achieve the same level precision and reproducibility of standard blood collection methods. Our collaborators at Northwestern University have pioneered this technique as leaders in the development, validation and application of whole dried blood spots as a convenient means for collecting, transporting, and processing blood samples from community settings and mind-body intervention research including clinical trials.

Measured Outcomes: The primary outcomes are feasibility and acceptability of the intervention and research procedures. Study staff will record all feasibility outcomes throughout recruitment, screening, enrollment, and the intervention, data collection, and follow-up phases.

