Feasibility outcomes for recruitment include: $\geq 70\%$ of patients reached consent to screening, $\geq 70\%$ meet screening criteria, $\geq 70\%$ of eligible enroll, and enrolling approximately N=20 participants within 1-2 months. Feasibility for eligibility criteria include: $< 20\%$ ineligible due to each criterion, reasons for ineligibility, reasons for refusal, and characteristics of refusers. MBCT feasibility will be measured by: $\geq 75\%$ session attendance, $\geq 75\%$ post-assessments completed, $\geq 70\%$ follow-up assessments completed, fidelity checklist score $\geq 80\%$, and $\geq 75\%$ complete home practice at least 3 days/week. Videoconferencing feasibility will be assessed by: $< 20\%$ of connections dropped during session; $< 20\%$ of sessions missed due to technical problems; number (Mean < 2.0) and types of problems, $< 20\%$ ask for extra training and type of extra training needed. Blood spot feasibility will be assessed by $\geq 75\%$ of samples submitted at baseline and post-intervention, $\geq 60\%$ submitted at follow-up, and 80% of samples of adequate quality.

Acceptability outcomes will be assessed via post-session surveys, post-intervention surveys, and exit interviews. MBCT acceptability will be assessed by average scores ≥ 7.5 on ratings of session helpfulness, enjoyment, relevance, and utility of session components (scale of 1 = not at all to 10 = very much). Overall program satisfaction will be assessed by $M \geq 7.5$ regarding overall program satisfaction, $\geq 75\%$ of participants reporting that they plan to use the skills in the future, $\geq 75\%$ reporting that they would recommend the program to others, and $\geq 60\%$ reporting continued mindfulness practice on the follow-up survey. Likes and dislikes will be explored in the exit interviews. Videoconferencing acceptability will be assessed in terms of ease and

confidence of use (1 = not at all to 10 = extremely, $M \geq 7.5$), interference of technical problems (1 = none to 10 = extreme, $M < 2.0$), audiovisual quality and overall satisfaction (1 = poor to 10 = excellent, $M \geq 7.5$), and themes related to pros and cons and suggestions for improvement in the exit interviews. Blood spot acceptability will be assessed by ratings of ease of data collection and submission (1 = not at all, 10 = extremely; $M \geq 7.5$), level of pain (1 = none, 10 = extreme, $M < 2.0$), and concerns and suggestions for improvement expressed in the exit interview.

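### Does letting the SAP summarise ratings by mean or median leave the acceptability cut-offs undefined?

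*SAP*

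**What the plan says.** The Protocol, under Measured Outcomes, states that "The primary outcomes are feasibility and acceptability of the intervention and research procedures". For session ratings, "MBCT acceptability will be assessed by average scores" of at least 7.5 on a 1–10 scale. Overall satisfaction, the favourable videoconferencing ratings and ease of blood spot collection carry a cut-off of M at or above 7.5. Technical interference and blood spot pain carry M below 2.0. In the same section the cut-off for the number of videoconferencing problems is written with the word Mean in full, so M can only be the mean.

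Three further acceptability items are percentages: at least 75% "of participants reporting that they plan to use the skills in the future", at least 75% who would recommend the programme, and at least 60% "reporting continued mindfulness practice on the follow-up survey". The sources are given too: "Acceptability outcomes will be assessed via post-session surveys, post-intervention surveys, and exit interviews". A survey follows each of the eight sessions (Post-session surveys).

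SAP Section 6.2 describes a small single-arm pilot and adds "As such the analyses are focused on descriptive statistics". For the ratings it says "Means and standard deviations or medians and interquartile ranges will be calculated to assess acceptability ratings". It then lists the constructs, for example "MBCT acceptability (helpfulness for mood; usefulness of session components", without numerical cut-offs. One part of the SAP was not supplied, so any statement here about what the SAP lacks covers only the supplied text.

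**The concern.** A primary outcome with numerical benchmarks should have a defined statistic. Read alone, the SAP sentence allows a report that gives medians only. Such a report would comply with the SAP and still leave the Protocol's mean-based benchmarks unassessed. Bounded ratings are usually skewed, so mean and median can fall on opposite sides of a cut-off, and at 7.5 the median is usually the more favourable.

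A second choice is open. Neither document says whether session ratings are pooled over all surveys, averaged within each participant first, or averaged by session. With a 75% attendance target, numbers of ratings per person will differ, and people who attend little may rate lower. At stake would be whether a benchmark is reported as met, and so how the acceptability result informs refinements before the pilot RCT.

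**Working it through.** The plan derives no figure for these ratings, so there is nothing to reproduce. Enrolment is about 20 with 20% expected loss, which gives 20 × (1 − 0.20) = 16 raters. The documents give no expected mean or SD, so every rating pattern below is an assumption.

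**1. Can mean and median disagree?** Yes.
- Ten ratings of 8 and six of 6: mean (80 + 36)/16 = 7.25 (misses 7.5); median 8 (meets).
- Pain, eleven ratings of 1 and five of 5: mean (11 + 25)/16 = 2.25 (misses < 2.0); median 1 (meets).

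**2. How often?** Simulation of 40,000 samples of 16 beta-binomial ratings on 1–10, three assumed spreads, cut-off 7.5:

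| True mean | SD range | Verdicts differ |
|---|---|---|
| 7.0 | 1.94–2.71 | 25–37% |
| 7.5 | 1.85–2.57 | 25–31% |
| 8.0 | 1.71–2.39 | 8–15% |
| 8.5 | 1.54–2.14 | 1–3% |

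Most disagreements have the median meeting and the mean missing. For pain at a true mean of 2.0 the verdicts differ in about 31–42% of samples. The pain cut-off is the more sensitive one: at a true mean of 2.5 they still differ in 22–46%.

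**3. Does either document compare a median with a cut-off?** Put side by side, the Protocol gives every rating cut-off and attaches each to an average or M. The SAP gives no cut-off and names two customary pairs of descriptive summaries. The two do not conflict: the Protocol supplies the benchmark and its statistic, and the SAP says how ratings will be described. The frequencies in step 2 apply only to an analyst who replaces the Protocol's statistic with another.

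**4. Order of averaging.** Let regular attenders rate 8 at all eight sessions and low attenders rate r. Let a be the low attenders' share of participants and b their share of ratings.

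Pooled mean = 8 − (8 − r)b; participant-level mean = 8 − (8 − r)a; difference = (8 − r)(a − b).

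With r = 6:

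| Pattern | a | b | Pooled | Participant-level | Reverses at 7.5? |
|---|---|---|---|---|---|
| 12 attend 8, 8 attend 3 | 8/20 = 0.400 | 24/120 = 0.200 | 7.60 | 7.20 | Yes |
| 11 attend 8, 5 attend 4 | 5/16 = 0.313 | 20/108 = 0.185 | 7.63 | 7.375 | Yes |
| 12 attend 8, 4 attend 4 | 4/16 = 0.250 | 16/112 = 0.143 | 7.71 | 7.50 | No |
| 15 attend 8, 5 attend 2 | 5/20 = 0.250 | 10/130 = 0.077 | 7.85 | 7.50 | No |

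In the first pattern, pooled ≥ 7.5 needs 768 + 24r ≥ 900, so r ≥ 5.5. Participant-level < 7.5 needs 96 + 8r < 150, so r < 6.75. The reversal window is 1.25 points. In the second it runs from 5.3 (704 + 20r ≥ 810) to below 6.4 (88 + 5r < 120), or 1.1 points. If everyone rates all eight sessions, a = b and the two means are identical.

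**5. Size against sampling error.** With 16 raters the 95% half-width of a mean is 2.131 × SD/√16: 0.80 at SD 1.5 and 1.07 at SD 2.0. The shifts in step 4, about 0.2–0.4 points, are smaller than either.

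**The case for a change.** The strongest reply is that a statement costs almost nothing and removes a choice that could be made after the data are seen, usually in the favourable direction at 7.5. If the Protocol governs, the SAP could say so, and the Protocol itself gives no order of averaging. Nobody can know in advance that results will lie far from 7.5 or 2.0. Intervals would also show how little 16 raters can establish: 12 of 16 has an exact 95% interval of 48–93%. And the SAP's acceptability list leaves out the Protocol's three percentage items.

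Part of this stands. The order of averaging is unspecified in the supplied text, and naming one would be good practice. The rest does not amount to a defect. The hazard with medians requires setting aside a statistic that the Protocol writes down. Pooled, participant-level and per-session averages are each reasonable, so preferring one does not correct an error. Intervals would change no verdict reached on a point estimate, and where a mean is reported with its SD, a reader who knows the number of raters can form one as in step 5. The percentage items remain defined in the Protocol, and because they are survey reports, those who answered are the natural base.

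A separate matter is the rating scale: the SAP describes 0–10 with higher meaning more acceptable, while the Protocol uses 1–10 with low values favourable for pain and interference. That does not bear on mean versus median and is not settled here.

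**Conclusion.** No change follows. The Protocol fixes the mean as the figure compared with each rating cut-off, and the SAP's wording is ordinary descriptive language that does not displace it. The missing order of averaging is a detail analysts can fill sensibly: it changes nothing when numbers of ratings are equal, moved the mean by about 0.2–0.4 points in the unequal patterns tried, and reverses a verdict only when the cut-off lies inside that gap.

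The consequence is limited to how a benchmark is reported in a descriptive pilot. No hypothesis test or go/no-go rule is tied to these ratings, and exit interviews also inform acceptability. The conclusion rests on reading the Protocol and SAP together and on assumed rating distributions. Close to a cut-off the choice of statistic would matter in roughly a quarter or more of samples, and that choice is the one the Protocol has already made.
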